After an overnight fast (> 10 hours), study subjects will report to LSU Exercise Physiology Laboratory to complete V4. V4 will be scheduled 48 hours after the subject's last training session. During this visit, we will measure height, weight and vital signs. During this visit, we will ask subjects to complete the International Physical Activity Questionnaire-Elderly,¹⁹ Sedentary Behavior Questionnaire,²⁰ and PROMIS Physical Function Questionnaire^{21, 22}, and the Pittsburgh Fatigability Questionnaire. We will also measure the body composition by DXA and BIA. We will also perform the MMTT as described for V1. We will also draw fasting and MMTT associated bloods as described for V2 (total blood volume of about 150 ml or 10-12 tablespoons total). The analyses performed on these blood samples collected in V4 will be as described for V2.

Posttraining V5 (About 3.5-4 hours)

After an overnight fast (> 10 hours), study subjects will report to PBRC to complete V5. V5 will be scheduled about 72 hours after the subject's last training session. During this visit, we will measure height, weight and vital signs. We will measure body composition using standard circumferences, optical imaging, and BIA, which will be conducted in [name] Laboratory. During this visit, we will collect a fasting blood sample (~ 10 ml). We will also perform the MRI for leg muscle mass, Phosphorous Magnetic Resonance Spectroscopy – ³¹P-MRS, and Muscle Biopsy as described for V3. During V5, subjects who agree to the optional Carbon-13 magnetic resonance spectroscopy procedure will do that procedure.

STUDY ENDPOINTS

Primary Endpoints

1. Comparison of within and between group changes in muscle strength, mass, and quality (strength/mass) using isokinetic dynamometry and DXA (primary outcomes Aim 1) between treatment groups.
2. Comparison of within and between group changes in body composition by DXA, fasting blood glucose and lipids by a clinical chemistry panel and glucose tolerance by a mixed meal tolerance test (primary outcomes Aim 2)

Safety Endpoints

1. Safety will be monitored by adverse event reporting (See Data Safety Monitoring Plan).

DETAILED METHODS AND ANALYSIS

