[name] (LSU) and [name] (PBRC). We will screen all data for distributional properties (mean, median, range) and departures from normality prior to substantive analyses. To test the main effects of time, treatment, and their interaction on the primary outcomes, we will use mixed-effects two-way Analysis of Variance (ANOVA) models ($\alpha=0.05$). The models will include parameters to estimate the main effects of time (pre- and post-training) and treatment (RE, REALPA breaks in ST, RE+AE) on the dependent variables. We will use *Fisher's Least Significant Differences test* to examine within and between group mean differences ($\alpha=0.05$). We will test all models for the main effect of sex. If the main effect of sex is significant, we will perform additional exploratory analyses stratified by sex. Other covariates that may be included in the models include race, change in body weight, and baseline SPPB scores. We will also compare adherence rates across the study groups.

Sample Size, Power Analysis and Randomization. We will use the data collected in this **pilot study** to estimate effect sizes for the primary and secondary outcomes, which we will use to inform our power analyses for a follow-up R01 application designed to test the efficacy of our novel exercise intervention on skeletal muscle and cardiometabolic health in sedentary older adults. We will use a fixed sample size of 12 subjects per group, because increasing the sample size above 12 (i.e., 12 to 15) has diminishing benefit in estimations effect sizes and 95% confidence intervals often referred to as the “rule of 12”.^{39, 40} Thus, we will recruit up to 15 subjects per group to account for a 20% attrition rate. The NIH’s Clinical and Translational Science Awards Biostatistics, Epidemiology, and Research Design (BERD) units recommend 12 subjects per group for estimating effect sizes and 95% confidence intervals.³⁹ Following baseline testing, we will randomize the study subjects to one of the three interventions using a randomized, permuted, block design stratified by sex and race.

PROVISIONS TO MONITOR THE DATA TO ENSURE THE SAFETY OF SUBJECTS

This Human Subjects Research meets the definition of a Clinical Trial. This study does not involve major risk to subjects. Efforts to minimize the potential risks of the assessment methods and outcome variables include frequent monitoring by the investigators to assure that no volunteer suffers any adverse effects from participating in the research.

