Retention Strategies. Retention will be a challenge in the proposed studies, as it is in all clinical trials. Our proposed study provides a variety of benefits in an effort to maximize the number of subjects who complete all follow-up visits. These benefits include the interventions and medical monitoring. Essential aspects of maximizing participation and promoting retention are: 1) carefully screening and assessing barriers to adherence and retention prior to randomization; 2) carefully monitoring adherence problems (which often predict retention problems), trying to identify these problems early before subjects refuse further study contact; and 3) applying specific strategies to address these problems. Some strategies include providing social and emotional support, flexibility in scheduling exercise training session and flexibility in scheduling study visits.

Randomization. After completing both pre-training visit 1 and 2, study subjects will be randomized to one of three 12 week intervention groups i) RE alone, ii) REALPA breaks in sedentary time, or iii) RE+AE. We will prepare randomization scheme based on a permuted block design stratified by sex and race.

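### The randomisation strata, sex and race, are not committed to the model of change; if they predict the change, the intervals for between-arm differences are wider than the design allows

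*Combined protocol and SAP*

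**What the plan says.** The section Sample Size, Power Analysis and Randomization allocates subjects "using a randomized, permuted, block design stratified by sex and race". The Randomization paragraph under Risks to Human Subjects repeats this: "based on a permuted block design stratified by sex and race".

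The section Data Management and Primary Statistical Analyses sets out a mixed-effects two-way ANOVA that tests time, treatment and their interaction: "The models will include parameters to estimate the main effects of time (pre- and post-training) and treatment". On the first stratum it says: "We will test all models for the main effect of sex". The stated consequence is limited: "If the main effect of sex is significant, we will perform additional exploratory analyses stratified by sex". The second stratum appears only in a list of possible additions: "Other covariates that may be included in the models include race, change in body weight, and baseline SPPB scores". There is no rule for when race enters, no statement of whether sex stays in the final model, and no term for sex by time or race by time.

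The endpoints are changes. The first under Study Endpoints begins: "Comparison of within and between group changes in muscle strength, mass, and quality (strength/mass) using isokinetic dynamometry and DXA". The sample size of 12 completers per group is justified by estimation of effect sizes and 95% confidence intervals, not by power.

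**The concern.** Stratified randomisation makes the arms more alike on sex and race than chance would. If either factor predicts how much a subject changes, the between-arm difference in change varies less from trial to trial than under simple randomisation. An analysis that ignores the strata leaves that variation in the error term, so its interval does not reflect the precision that the design has secured.

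The form of the adjustment matters as much as its presence. In a pre/post model with a subject effect, stable differences between men and women or between race groups cancel out of the change. A main effect therefore does no work for the contrast of interest. Only a stratum-by-time term, or equivalently the stratum as a covariate in a model of change, removes stratum differences in response.

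Two things are at stake. The pilot's main product is a set of effect sizes with 95% intervals for planning a larger trial, so avoidable width is a direct cost. And because race is discretionary, it could enter the models for some primary outcomes and not for others.

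**Working it through.** **Inputs from the documents.** Three arms; 12 completers per arm, 36 in total; up to 45 randomised with 20% attrition; strata sex and race; alpha 0.05, taken as two-sided.

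**Assumptions, because the documents give no figure.** Two race levels; small blocks; R², the share of the variance of change explained by sex and race together, between 0 and 0.30.

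**The plan's own figure.** 12 / (1 − 0.20) = 15 per group, and 3 × 15 = 45. This reproduces. The plan states no interval width or power to reproduce.

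**Step 1: do main effects help?** Simulated pre/post data sets (40 per scenario) were fitted by REML with a random subject intercept. Mean standard error of a time-by-treatment contrast:

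| Scenario | No strata | Sex + race main effects | Sex and race, each by time |
|---|---|---|---|
| Strata affect level only, complete data | 0.2204 | 0.2204 | 0.2192 |
| Strata affect level and change, complete data | 0.2540 | 0.2540 | 0.2192 |
| Level only, 45 randomised, 9 without a post value | 0.2302 | 0.2295 | 0.2291 |

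With complete data, the estimates with and without main effects agree to about 10⁻¹⁵. With missing post values, main effects move the standard error by (0.2302 − 0.2295) / 0.2302 = 0.3%. When the strata affect change, only the by-time terms reduce it.

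**Step 2: interval width, balanced cells.** The half-width for a difference in change, in SDs of change, is t(df) × √[(2/12)(1 − R²)]. Unadjusted, df = 36 − 3 = 33 and t = 2.0345, which gives 2.0345 × √(2/12) = 0.831. Adjusted, df = 31 and t = 2.0395.

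| R² | Adjusted half-width | Change from 0.831 |
|---|---|---|
| 0 | 0.833 | +0.2% |
| 0.05 | 0.812 | −2.3% |
| 0.10 | 0.790 | −4.9% |
| 0.20 | 0.745 | −10.3% |
| 0.30 | 0.697 | −16.1% |

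Break-even is R² = 1 − (2.0345/2.0395)², about 0.005.

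This formula slightly understates the gain. With exact balance, the whole stratum sum of squares falls into the unadjusted error, whose expected mean square is (1 − R²) + R² × 36/33. At R² = 0.30 that is 0.700 + 0.327 = 1.027, and the width ratio becomes (2.0395/2.0345) × √(0.700/1.027) = 0.828, or 17% narrower. Simulation of 20,000 balanced trials per R² gave 5.3%, 11.3% and 17.3% narrower at R² = 0.10, 0.20 and 0.30.

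**Step 3: coverage of the unadjusted 95% interval.** The same balanced simulation gave 95.0% at R² = 0, and 96.2%, 97.2% and 98.2% at 0.10, 0.20 and 0.30.

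**Step 4: a less ideal trial.** Here 45 are randomised in blocks of 3 or 6, 9 are lost at random, and the splits are 60/40 by sex and 80/20 by race (all but the 45 and the 9 assumed). Adjustment narrows the interval by about 4%, 10% and 16% at the same three R² values. Unadjusted coverage is about 95.9%, 96.4% and 97.3%. At R² = 0, adjustment widens the interval by just over 1%.

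**For scale.** The plan considers going from 12 to 15 per group. That changes the width by a factor of about √(12/15) = 0.894, or 11% narrower, close to what adjustment gives at R² = 0.20.

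**The case against.** The strongest reply is that nothing shows the intervals to be too wide. That requires sex or race to predict the training response, not merely the level of strength or lean mass. The documents give no such figure, and one R² cannot stand for strength, body composition, fasting glucose, lipids and meal tolerance alike. This stands: the size is conditional throughout, and at R² = 0 adjustment is slightly harmful.

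Second, the wording about other covariates can be read as placing sex in every model already. That reading is fair but does not help, since a sex main effect leaves the contrast of change untouched. The sex-stratified analyses do not fill the gap either: they are exploratory and depend on a test of sex differences in level.

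Third, block size and the number of race levels are not stated, and a rare race group would weaken both the balance and the gain. This also stands.

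A reader might infer three stronger things, none of which the documents support:

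- That the stratification is wasted. Balance between arms holds whatever model is fitted; only a possible gain in precision is missed.
- That the planned intervals are invalid or the false-positive rate is raised. Ignoring the strata introduces no bias here, and coverage is at or above nominal.
- That the optional status of race is itself what widens the intervals. Making race a compulsory main effect would recover essentially nothing; the missing element is the interaction with time.

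**Conclusion.** The mismatch is real: the plan stratifies by sex and race but does not commit its model of change to either factor in a form that could affect the comparison between arms. The unadjusted interval is valid but conservative.

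Under two race levels, small blocks and 36 completers, with assumed R² of 0.10, 0.20 or 0.30, adjustment narrows the interval by about 4–5%, 10–11% or 16–17%. The unadjusted 95% interval covers about 96%, 96–97% or 97–98%. If the strata explain nothing, adjustment widens the interval by about 0.2% with balanced cells and about 1% with unequal strata and attrition.

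The algebra on main effects is certain for complete data and nearly exact with the planned attrition. Whether any width is actually lost depends on quantities that the documents do not give. The change is worth making because the possible gain is moderate, the possible loss is small, and it removes analyst discretion over race.

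**What to change.** In Data Management and Primary Statistical Analyses, state that every primary-outcome model includes sex and race, at the levels used for randomisation, each with its interaction with time, whatever their p-values. With two time points and complete data this is equivalent to entering both as covariates in a model of change. Remove race from the list of optional covariates, and state the race levels used for stratification.

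The cost is a sentence or two of analysis-plan wording and 2 degrees of freedom with two race levels; more levels would cost more. No new data are needed, since both factors must be known to randomise.

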Screening Visit, Part II (about 2 hours) will be conducted in LSU Exercise Physiology Laboratory and will include height, weight, the completion of the International Physical Activity Questionnaire-Elderly,¹⁹ Sedentary Behavior Questionnaire,²⁰ and PROMIS Physical Function Questionnaire^{21, 22}, and the Pittsburgh Fatigability Questionnaire. We will also measure height and weight. We will measure isokinetic strength and endurance of the knee extensors (Biodek System 3) and the 1-repetition maximums (1-RMs)

for the knee extension, leg press, and chest press. Note: the 1-RM measurements may be performed prior to your regularly scheduled exercise session during the first and last week of the intervention. We will also measure grip strength using a hand dynamometer.

Baseline Physical Activity Monitoring. At the end of part II of the screening visit, all subjects who are deemed eligible to continue onto the pre-training visits described below will be provided two devices to measure their physical activity leading up to their pre-intervention testing. A wrist-worn physical activity monitor (Actigraph, GT9X) will be issued to the subjects to wear 24-h/d for 7-days (± 3 days) prior to their pre-training visits to quantify objectively their PA and ST. Subjects will also be asked to wear a second physical activity monitor (Actigraph, GT9X) on their thigh 24-h/d for 7-days (± 3 days). Subjects will be asked to return their physical activity monitors during the Pre-training Visit 1 (V1). In the event that a subject is deemed ineligible after part II of the screening visit, we would request that the subject return his/her physical activity monitors at their earliest convenience. We will screen raw data from these monitors for periods of valid wear-time with a required minimum wear-time of 10 h per valid wear-day and 4 valid wear-days per week.^{23, 24} We will use standard algorithms to characterize the patterns of PA and ST.²⁵

Baseline Dietary Record. Subjects will be asked to record their dietary intake for the 24 hrs prior to their pretraining visit 1. They also will be asked to replicate their dietary intake before posttraining visit 4. Moreover, they will be asked to refrain from consuming caffeine or participating in vigorous exercise 48 hours prior to these visits.

Pre-training Visits 1 (V1). (About 5 hours). V1 will be scheduled at least 7 days after screening visit Part II.

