After an overnight fast (> 10 hours), subjects will report to the LSU's Exercise Physiology Laboratory to complete V1. During V1, we will measure height, weight and vital signs. We will measure body composition using Dual Energy X-Ray Absorptiometry (DXA) (Hologic, Horizon A)¹⁵ and bioelectrical impedance analysis (BIA). During V1, we will acquire a fasting blood sample (~50 ml or 10 teaspoons) for the measurement of glucose, insulin, lipids, pro-inflammatory cytokines, and isolation of T-cells. We will then perform a standardized Mixed Meal Tolerance Test (MMTT) with serial blood draws (~100 ml total or 6.8 tablespoons) to measure glucose and insulin area under the curves (AUCs), insulin sensitivity (SI), and beta cell responsivity (Φ).²⁶ We will draw about 150 ml or 10-12 tablespoons of blood for this test in total. We will use a portion of the fasted blood samples collected to characterize each subject's immune compartment using four-color flow cytometry,²⁷⁻²⁹ while also assessing negatively-sorted T-cell OXPHOS using HRR.

Pre-training Visits 2 (V2). (About 3.5-4 hours). V2 will be scheduled at least 24 hours after V1, but within 2 weeks of V1.

After an overnight fast (> 10 hours), study subjects will report to PBRC to complete V2. During V1, we will measure height, weight and vital signs. We will measure body composition using standard circumferences, optical imaging, and BIA, which will be conducted in [name] Laboratory. During V2, subjects will undergo a magnetic resonance imaging (MRI) study to measure leg muscle mass and phosphorus magnetic resonance spectroscopy (^{31}P -MRS), to measure *in vivo* mitochondrial oxidative capacity.³⁰ During V2, subjects who agree to the optional Carbon-13 magnetic resonance spectroscopy procedure will do that procedure. During V2, a percutaneous muscle biopsy from the *vastus lateralis* (~500 mg) will be acquired under local anesthesia to assess muscle OXPHOS using HRR,^{15, 31} mitochondrial enzyme activities, and oxidative damage to muscle proteins by immunoblotting. Note: the muscle biopsy will be acquired from the opposite leg, as the MRS study was performed.

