11. **Muscle Biopsies.** A *vastus lateralis* muscle biopsy will be performed using the technique of Bergstrom as described in SOP 906 from the PBRC Inpatient Unit by a trained Nurse Practitioner or physician. For *vastus lateralis* muscle biopsies, the risks are mild to severe pain, soreness, bruising and a small scar are common risks. There is a small risk of a hematoma (collection of blood in the tissue) or infection at the biopsy site. There is also a slight risk that a superficial nerve may be cut; the nerve may heal, or it may result in a permanent loss of sensation in the skin at the biopsy site. Sterile technique will be used to minimize infection risks and the biopsy site will be monitored closely. To reduce the risk of hematomas and bleeding, we ask that subjects stop taking anticoagulants, non-steroidal anti-inflammatory (NSAIDs), and aspirin for a week before and after the biopsy procedure. We will exclude individuals who cannot stop their anticoagulants. Previous data suggest that the rates of adverse events following a percutaneous muscle biopsy in older adults (60-76 years) are similar to those of younger adults.⁴¹ Moreover, [name] previously conducted a study at PBRC that included biopsies in elderly adults (70-84 years) with no serious adverse events.⁴² The PI has led and been involved in multiple studies that included muscle biopsies in both young (18-30) and older adults (65-85 years).^{15, 43-45}
12. **Archive of Biological Sample (blood and muscle biopsy tissue).** The primary risk to subjects who donate bio-samples to be banked for future research (molecular in this case) is the risk of loss of confidentiality and/or privacy. Most banks need to maintain a link between the identities of donors and coded specimens to be able to collect valuable clinical follow-up information about the donor. We will, however, create and maintain a firewall between the source and the researcher so that the protected health identifiers are never given to the researcher(s). Storage and disposal of tissue will be conducted in a manner conforming to the appropriate care and handling of biological specimens as outlined through the Institutional Biohazard Committee Guidelines.

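### The one-week NSAID/aspirin stop is timed to the biopsies, so a regular user can be about 6 days off drug at the post-training meal test and 0 to 6 days off at baseline

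*Combined protocol and SAP*

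**What the plan says.** The drug stop is in the Potential Risks section, item 11 (Muscle Biopsies): "we ask that subjects stop taking anticoagulants, non-steroidal anti-inflammatory (NSAIDs), and aspirin for a week before and after the biopsy procedure". The only reason given there is to limit bleeding and hematoma.

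At baseline, the MMTT, fasting blood and cytokine sample are taken at V1 and the biopsy at V2. The V2 section sets the spacing: "V2 will be scheduled at least 24 hours after V1, but within 2 weeks of V1". After training, the V4 section says "V4 will be scheduled 48 hours after the" last training session and, of the meal test, "We will also perform the MMTT as described for V1". The second biopsy is at V5, and "V5 will be scheduled about 72 hours after" that same session.

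The Baseline Dietary Record paragraph has subjects repeat their pre-V1 diet before V4 and adds: "Moreover, they will be asked to refrain from consuming caffeine or participating in vigorous exercise 48 hours prior to these visits". It says nothing about NSAIDs or aspirin.

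The second primary endpoint is "Comparison of within and between group changes in body composition by DXA, fasting blood glucose and lipids by a clinical chemistry panel and glucose tolerance", the last of these measured with the MMTT. Systemic inflammation is a secondary outcome under Aim 2.

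The medication exclusion does not name NSAIDs or aspirin, but its list is illustrative, not closed. The section on human subjects' characteristics keeps subjects on their current drugs, except those known to interact with the outcomes.

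**The concern.** The plan takes care that V1 and V4 are comparable: both are fasted, diet is replicated, caffeine and hard exercise are withheld, and medication must be stable for 30 days before entry. The biopsy instruction then changes drug intake around the same visits, on a clock tied to V2 and V5. Because the two biopsies sit at different distances from their meal tests, the same instruction can leave a subject in one drug state at baseline and another after training.

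What is at stake is the pre-post change within a group. The endpoints name within-group change, the analysis section tests the effect of time and within-group differences, and the pilot is meant to supply effect sizes for a larger trial. The listed covariates do not include medication use.

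**Working it through.** **Inputs.** Stop length before a biopsy: 7 days (Muscle Biopsies item). V1-V2 gap *g*: 1 to 14 days (V2 section). V4 and V5: 48 h and about 72 h after the last session (V4 and V5 sections). The V5 text refers to V3 for the biopsy method, although the method is described under V2; this does not affect the timing. The plan gives no figure of its own to reproduce.

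**Formula.** Days off drug at a meal test = max(0, 7 − days from that test to the next biopsy).

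**V4.** Gap to biopsy = (72 − 48)/24 = 1 day, so days off = 7 − 1 = 6. If the V5 timing is allowed to run from 60 to 84 h (an assumed tolerance), the result is 7 − 0.5 = 6.5 to 7 − 1.5 = 5.5 days.

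**V1.** Days off = max(0, 7 − *g*):

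| V1-V2 gap (days) | Days off at V1 | Days off at V4 | V4 minus V1 |
|---|---|---|---|
| 1 | 6 | 6 | 0 |
| 2 | 5 | 6 | 1 |
| 3 | 4 | 6 | 2 |
| 4 | 3 | 6 | 3 |
| 5 | 2 | 6 | 4 |
| 6 | 1 | 6 | 5 |
| 7 to 14 | 0 | 6 | 6 |

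Only a 1-day gap matches exactly. Eight of the 14 whole-day gaps leave the subject with no days off at V1; that is a count of permitted gaps, not a probability. At the nominal timings the difference is never negative, so differences in days off do not cancel across users.

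**With V2 at 24 to 48 h after V1.** *g* = 1 to 2, so days off at V1 = 6 to 5, against 6 at V4. The difference is 0 to 1 day.

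**Measurements outside the meal-test visits.** For V1, "V1 will be scheduled at least 7 days after screening visit Part II", so Screening Part II, with the baseline isokinetic test, is at least 7 + 1 = 8 days before V2 and always precedes the stop. The clinical chemistry panel is drawn at Screening Part I and at V5. That is before the stop at baseline, provided Part I is no later than Part II, and 7 days into it after training. Moving V2 closer to V1 changes neither.

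**Arms.** Randomisation follows V2, so assignment cannot influence the V1-V2 gap, and the stop and windows are the same for all three arms.

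**The case against.** The strongest reply is that days off drug are not bias. The documents nowhere say that a few days without an NSAID or aspirin alters glucose tolerance or cytokines. If such a drug is known to affect the outcomes, the open-ended medication exclusion already reaches its user. The vascular and renal exclusions, and those for arthritis or orthopedic limits that preclude exercise, thin the group further. The request also covers anticoagulants, which are excluded anyway, so it may be stock safety wording and not a sign that users are expected. The hypothesis is a contrast between arms, and with no non-exercising arm the within-group change is already open to time and repeat-testing effects. Finally, a 24 to 48 h window for up to 45 subjects across two sites would be a heavy demand.

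Much of this stands. It rules out any statement about effect size or direction, and it argues against a tighter window for everyone. It does not remove the mismatch: no section aligns drug state between V1 and V4, NSAIDs and aspirin are not named as exclusions, and the stop request itself provides for subjects who take them.

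A reader might infer three stronger things. One is that the comparison between arms is biased. The common stop and randomisation after V2 do not support that; chance imbalance is possible with 12 completers per arm, but no systematic shift is expected. Another is that the training effect is exaggerated or masked in a known direction. The documents give no drug effect from which to say so. The third is that week-16 strength is taken a definite number of days into the stop. Session days are flexible and up to two weeks may be added, so no such count can be fixed.

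**Conclusion.** The timing mismatch is real: for a complying regular user, about 6 days off drug at V4 against 0 to 6 at V1, with the full 6-day difference whenever V2 falls 7 to 14 days after V1. Within-group change in MMTT glucose tolerance and in inflammatory markers can therefore combine training with a change in drug state in those subjects.

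This assumes that some regular users are enrolled, that they follow the request for exactly the stated week, and that V5 is close to 72 h. The share of users is not given and may be small; the effect on any outcome is not given at all. This is an inexpensive improvement to consider, not a threat to the trial's main question.

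**What to change.** In the V2 section, add that for subjects who report regular NSAID or aspirin use at screening, V2 is scheduled 24 to 48 hours after V1. All other subjects keep the window of 24 hours to 2 weeks. The new spacing lies inside the present window and mirrors the roughly 24 h between V4 and V5. The bleeding-safety instruction and the post-training visits stay as they are.

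The cost is one sentence and tighter scheduling for those subjects only: two fasting visits close together, V1 at LSU and V2 at PBRC, as V4 and V5 already are.

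The change does not address strength testing or the Screening Part I versus V5 chemistry panel, which is the named source of primary fasting glucose and lipids. As optional support, record the date of the last NSAID or aspirin dose at V1 and V4, if the forms do not already hold it. Then describe change in glucose AUC and inflammatory markers with and without regular users, with no test attached.
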